4 ANALYSIS POPULATIONS

4.1 Intent-to-Treat Population

The intent-to-treat (ITT) population will consist of all randomized subjects regardless of whether or not the subject received test article.

A subject is considered randomized when the IxRS provides the test article assignment by providing the kit number (ie, completes a randomization transaction). Subjects in this population will be summarized according to randomized test article assignment.

4.2 Safety Population

The Safety population will consist of all randomized subjects who receive any amount of test article. All safety analyses will be conducted in this population. Subjects in this population will be summarized according to actual test article received.

4.3 Microbiological Intent-to-Treat Population

The microbiological Intent-to-treat (micro-ITT) population will consist of subjects in the ITT population who have a study-qualifying pre-treatment Baseline urine culture with 1 or 2 uropathogens at $\geq 10^5$ colony forming unit (CFU)/mL.

If more than two bacterial isolates are identified, the culture will be considered contaminated. Rules for Sponsor's determination of qualifying pathogens are described in the [Pathogen and CE Review Plan: PTK0796-uUTI-17201²](#).

4.4 Clinically Evaluable Population

The clinically evaluable (CE) population will consist of all ITT subjects who received test article, have a qualifying infection, an assessment of outcome, and meet all other evaluability criteria as described below.

Inclusion into the CE populations will be determined programmatically based on the data on the electronic case report form (eCRF) and a manual review by the Sponsor as necessary prior to unblinding. Details on allocation to each CE population are described in the [Pathogen and CE Review Plan: PTK0796-uUTI-17201²](#).

Since patient count may differ depending on timepoint, CE populations will be defined by milestone visit (CE-EOT, CE-PTE and CE-FFU).

To be included in the CE populations, subjects must meet all criteria defined below:

1. Qualifying infection:

- Exclusion Criterion #2, 3, and 4; Note: for subjects randomized after amendment 1 or later exclusions 3 and 4 are not applicable.

2. Assessment of outcome for CE population:

Subjects must meet all of the following to be included in any CE populations:

- Subject did not meet any of the exclusion criteria 1 and 7 through 10 in the protocol (Baseline event exclusion).
- Received the randomized test article and was at least 80% compliant with the dosing regimen (Compliance to test article intake).
- Study personnel involved in the assessment of efficacy remained blinded to study treatment, unless a treatment limiting AE occurred that required emergency unblinding.

In addition, for each endpoint the following needs to be satisfied, as appropriate:

a. For the CE-EOT population:

- i. Completed the investigator's assessment of clinical response (ie, was not deemed an indeterminate outcome) at the EOT visit

- ii. The EOT visit occurred on the day of, or within +2 days following the last dose of test article (3-day window).
- b. For the CE-PTE population:
 - i. The Overall Clinical Response (based on the investigator's assessment) at the PTE Visit is not Indeterminate (see [Table 5](#))
 - ii. The PTE Visit occurred on Day 14 (\pm 2 days) after the subject's first dose of test article, unless the subject was considered to be a Clinical Failure based on the investigator's assessment at the EOT visit.
- c. For the CE-FFU population:
 - i. The Overall (Sustained) Clinical Response (based on the investigator's assessment) at the FFU Visit is not Indeterminate (see [Table 6](#))
 - ii. The FFU Visit/Call occurred 30 to 37 days from the first dose of test article, unless the subject was considered to be a Clinical Failure based on the investigator's assessment at the PTE visit.

3. Other Evaluability Criteria

a. Prior Antibiotic Therapy:

Exclusion Criterion #5: Receipt of any dose of a potentially therapeutic antibacterial agent (with potential activity against uropathogens in the urinary tract) from 72 hours prior to randomization until the first dose of test article [Note: subjects who developed current cystitis while receiving prophylactic antibacterial therapy may be eligible if all prophylactic antibacterials are stopped]. Subjects who meet exclusion criteria #5 will be excluded from the CE populations.

b. Concomitant Antibiotic Therapy:

Subjects who receive any systemic concomitant antibiotic therapy that is potentially effective against the baseline pathogen from the start of administration of the first dose of test article through the EOT visit (CE-EOT population), PTE visit (CE-PTE population) or FFU visit (CE-FFU population) will be excluded from the CE populations. If no pathogen is isolated and the systemic concomitant antibiotic is effective against Gram-negative uropathogens, the subject will be excluded from the respective CE population. Subjects, who are a clinical failure on the particular visit and received non-study antibiotics for insufficient therapeutic effect of the test article, will not be excluded from the CE populations assuming they meet all other CE criteria. Subjects who receive a systemic concomitant antibiotic that is not potentially effective against the baseline pathogen will be included in the CE populations.

c. Evaluable Success and Failure

Evaluable success: The subject received at least 4 doses of active test article (omadacycline groups 1, 2, and 3) at least 6 doses of active test article (nitrofurantoin and omadacycline group 4) and the investigator classifies the subject as a Clinical Success at the EOT Visit (CE EOT population) or the overall Clinical Response (based on the investigator's assessment) at the PTE Visit (CE-PTE population) is Clinical Success.

Evaluable failure: The subject received at least 3 doses of active test article (omadacycline groups 1, 2, and 3) or at least 4 doses of active test article (nitrofurantoin and omadacycline group 4) and the investigator classifies the subject as a Clinical Failure at the EOT Visit (CE EOT population) or the overall Clinical Response (based on the investigator's assessment) at the PTE Visit (CE-PTE population) is Clinical Failure.

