6.2 Inclusion Criteria

Each subject must meet all of the following criteria to be enrolled in this study:

Main Criteria for Inclusion:

1. Written and signed informed consent must be obtained before any assessment is performed
2. Females age 18 years or older
3. Onset of 2 or more of the following clinical signs and symptoms of cystitis within 96 hours prior to randomization:
 - Dysuria
 - Frequency
 - Urgency
 - Suprapubic pain

NOTE: symptoms should be continuing at the time of randomization
4. A clean-catch midstream urine sample with pyuria (white blood cell [WBC] count > 10/ μ L in unspun urine or \geq 10 per high power field in spun urine) or dipstick analysis positive (at least ++) for leukocyte esterase. Urine sample must be sent for microbiologic culture prior to randomization.
5. Must have a negative pregnancy test at Screening, and agree to comply with using an acceptable form of birth control (eg, abstinence, oral contraceptive, intrauterine device [IUD], barrier contraception [condom], tubal ligation, hysterectomy, bilateral oophorectomy, postmenopausal or vasectomized partner) from Screening through PTE
6. Ability to swallow 4 tablets/capsules in succession
7. Ability to communicate well with the investigator, to understand and comply with the requirements of the study

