6.3 Exclusion Criteria

Patients who meet any of the following exclusion criteria will be excluded from the study:

Main Criteria for Exclusion:

1. Males
2. Pregnant or nursing (breastfeeding) women
3. *Criterion no longer applicable as per Protocol Amendment #1*
4. *Criterion no longer applicable as per Protocol Amendment #1*
5. Receipt of any dose of a potentially therapeutic antibacterial agent (with potential activity against uropathogens in the urinary tract) from 72 hours prior to randomization until the first dose of test article. [NOTE: Subjects who developed the current cystitis while receiving prophylactic antibacterial therapy (for any reason) may be eligible if all prophylactic antibacterials are stopped (no further dosing after randomization) and approved by the study medical monitor]
6. Anticipated need for systemic antibacterial therapy other than test article (for treatment or prophylaxis) during the study period
7. Has a suspected upper UTI (eg, fever $\geq 38^{\circ}\text{C}$, $\geq 100.4^{\circ}\text{F}$), chills, rigors, flank pain, or costovertebral angle tenderness)
8. Symptoms/signs suggestive of vaginitis or sexually transmitted infection (eg, vaginal discharge or vaginal irritation)
9. Known prior UTI caused by *P. aeruginosa* or *Proteus* spp., or suspected current infection with *P. aeruginosa* or *Proteus* spp. or nitrofurantoin-resistant pathogen
10. Has a confirmed or suspected complicated UTI, defined as:
 - Use of an indwelling urinary catheter, nephrostomy tubes or other indwelling urinary tract device within the 30 days prior to randomization or scheduled to be used during the study period
 - Known urinary retention (≥ 100 mL of residual urine after voiding) within the 30 days prior to randomization
 - History of surgically modified or abnormal urinary tract anatomy (eg, bladder diverticula or redundant urine collection system)
 - Complete or partial obstruction of the urinary tract, or obstructive uropathy that is scheduled to be medically or surgically relieved during the study therapy period
 - History of renal transplant or a surgically created intestinal conduit for urinary diversion
 - Suspected or confirmed renal calculi, stricture, primary renal disease (eg, polycystic renal disease), neurogenic bladder, or other anatomical or functional abnormalities predisposing to UTI
 - Had an overnight hospital stay within the past 6 months

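### The CE qualifying-infection condition (SAP 4.4 item 1) no longer describes an infection after Amendment 1, and no listed CE rule requires cystitis symptoms or pyuria (minor)

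*SAP*

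**What the plan says.** Protocol 12.3 and SAP 4.4 both require CE subjects to have a qualifying infection, as a condition separate from having an outcome assessment and meeting the other evaluability criteria. SAP 4.4 states that all the criteria it then defines must be met. Item 1, headed as the qualifying infection, reads in full: "Exclusion Criterion #2, 3, and 4; Note: for subjects randomized after amendment 1 or later exclusions 3 and 4 are not applicable".

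In Protocol 6.3, exclusion 2 is "Pregnant or nursing (breastfeeding) women". Exclusions 3 and 4 each read "Criterion no longer applicable as per Protocol Amendment #1".

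The remaining CE rules that cite entry criteria are in item 2 ("Subject did not meet any of the exclusion criteria 1 and 7 through 10 in the protocol (Baseline event exclusion") and item 3a ("Subjects who meet exclusion criteria #5 will be excluded from the CE populations"). The features that establish cystitis at entry are in Protocol 6.2. Inclusion 3 is "Onset of 2 or more of the following clinical signs and symptoms of cystitis within 96 hours prior to randomization"; inclusion 4 is pyuria or a leukocyte esterase dipstick of at least ++, with a urine sample sent for culture before randomization.

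SAP 4.4 also points outside itself. CE membership is set by program and by "a manual review by the Sponsor as necessary prior to unblinding", and "Details on allocation to each CE population are described in the" Pathogen and CE Review Plan.

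**The concern.** A condition named for the infection should test for the infection. From Amendment 1 on, item 1 tests only pregnancy and nursing. If nothing else in the CE definition asks for symptoms or pyuria, the written rule does not deliver the population it names, and a woman randomized in breach of inclusion 3 or 4 is carried into CE-EOT, CE-PTE and CE-FFU.

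At stake are the CE clinical success rates and their exact 95% intervals for the difference from nitrofurantoin (SAP 7.3.1), the ME results that build on CE (SAP 4.5), and the exploratory UTISA summaries in CE. Subjects without the target infection add outcomes that say little about the drugs. If they are equally common and respond alike in both arms, they pull the arms towards similarity.

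**Working it through.** **Cross-reference.** Each protocol criterion cited in SAP 4.4, matched to the current protocol text:

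| SAP 4.4 | Criterion cited | Content in Protocol 6.3 | Requires symptoms or pyuria? |
|---|---|---|---|
| Item 1 | Exclusion 2 | Pregnancy, nursing | No |
| Item 1 | Exclusions 3, 4 | Void since Amendment 1 | No, for later subjects |
| Item 2 | Exclusion 1 | Male sex | No |
| Item 2 | Exclusions 7 to 10 | Upper UTI; vaginitis or STI; certain pathogens; complicated UTI | No |
| Item 3a | Exclusion 5 | Prior antibacterial | No |

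For subjects randomized under Amendment 1 or later, the listed rules apply exclusions 1, 2, 5, 7, 8, 9 and 10 and no inclusion criterion. The other rules in 4.4 concern compliance, blinding, outcome and visit windows, concomitant antibiotics and minimum doses. For earlier subjects, inclusions 3 and 4 are not cited either. What former exclusions 3 and 4 required cannot be checked, because the documents do not give their text.

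**Reach.** Group 4 was added in Amendment 2, so the reduced item 1 applies to all of Group 4, while the other arms may include subjects from before Amendment 1. ME needs membership of both micro-ITT and CE (SAP 4.5), so there the gap is confined to subjects with a qualifying culture.

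**Illustration of size.** The plan states no figure to reproduce, and the documents give no violator count. Assumptions: true CE success is 82% on nitrofurantoin (the planning rate in Protocol 12.2, borrowed for CE) and 72% on omadacycline (lower by the 10-point margin). Violator fractions are qO (omadacycline) and qN (nitrofurantoin), and violators succeed at rate r. In points:

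Observed difference = [(1 − qO)·72 + qO·100r] − [(1 − qN)·82 + qN·100r]

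With qO = qN = q this is −10·(1 − q) for any r:
- q = 2%: −9.8 (shift 0.2)
- q = 5%: −9.5 (shift 0.5)
- q = 10%: −9.0 (shift 1.0)

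Violators in one arm only:
- 5%, nitrofurantoin, r = 0.50: 72 − (77.9 + 2.5) = −8.4
- 5%, nitrofurantoin, r = 0.95: 72 − (77.9 + 4.75) = −10.65
- 5%, omadacycline, r = 0.50: (68.4 + 2.5) − 82 = −11.1
- 5%, omadacycline, r = 0.95: (68.4 + 4.75) − 82 = −8.85
- 10%, nitrofurantoin, r = 0.50: 72 − (73.8 + 5.0) = −6.8 (shift 3.2)

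The sign depends on which arm holds the violators and how they respond.

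**Scale.** With 45 per arm (225/5) to 53 per arm, taken as assumed CE sizes, the approximate 95% half-width is 1.96·√[(0.72·0.28 + 0.82·0.18)/n]. This is 17.3 points at n = 45 and 15.9 at n = 53. Even the 3.2-point case is about a fifth of that.

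**The case against.** The strongest reply is that the SAP delegates the detail of CE allocation to the Pathogen and CE Review Plan and to sponsor review before unblinding. That plan may apply inclusions 3 and 4, so nothing here shows that the check is missing in practice. This stands as a limit on the claim. It does not repair the text: SAP 4.4 presents its own list as what subjects must meet, and that list gives the infection condition a content that is not about infection.

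Second, exclusions 7 to 10 do concern the infection, and they sit under a heading about outcome assessment, so the section may simply be badly sorted. That is partly fair. Those exclusions rule out other diagnoses, but none requires cystitis symptoms or pyuria.

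Third, harm is limited, and this stands in full. Sites confirm all criteria before randomization (Protocol 7.8). SAP 6.1 lists every randomized subject who failed a criterion, which criterion it was, and each subject's population membership, so violators in any CE set can be traced. SAP 6.6 reviews deviations under blind and tabulates major ones for CE-PTE. None of this removes a violator from CE.

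Fourth, violators in one arm only are unlikely, since eligibility is confirmed before assignment in a double-blind trial. The one-arm cases show what the formula can give; they are not forecasts.

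**Conclusion.** The point holds as a fault in the SAP text and is minor. For subjects under Amendment 1 or later, the qualifying-infection item reduces to pregnancy and nursing, and for all subjects the listed CE rules omit inclusions 3 and 4. Only secondary and exploratory CE and ME estimates are exposed. Inference on them is nominal (SAP 5.1.4), and SAP 7.3.1 attaches no non-inferiority rule to CE. The primary ITT comparison (SAP 7.2) is unaffected.

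Size and direction are unknown. Under the assumed rates the shift is 0.2 to 1.0 point for 2% to 10% violators in both arms, and about 3 points for 10% in the nitrofurantoin arm only with 50% success among them.

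Four stronger readings are not supported:
- That CE will in fact contain women without cystitis. The Review Plan is not available, and no violator is documented.
- That the Amendment 1 change log shows the symptom requirement moving from exclusion 3 to inclusion 3. The log says only that the onset timing in inclusion 3 was clarified and exclusion 3 removed; the former text is not given.
- That any shift is capped at 1.6 points. That cap appears only if one-arm cases stop at 5%.
- That the change took effect on 29 October 2018. That is the amendment's document date. Protocol 13.6.2 requires ethics approval before most amendments are implemented, so the effective date may be later and may differ by site.

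**What to change.** Before unblinding, reword SAP 4.4 item 1 along these lines: *Qualifying infection: had at least two of the listed cystitis signs/symptoms (Inclusion 3) and pyuria or positive leukocyte esterase (Inclusion 4) at baseline, under the protocol version in force at randomization; for subjects randomized before Amendment 1, also did not meet former Exclusions 3 and 4.*

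The sponsor should state, under blind, whether the 96-hour onset limit and the timing of culture dispatch count towards this condition. Requiring inclusions 3 and 4 in full would drop a symptomatic woman with pyuria only because her culture was sent late or her symptoms began slightly too early. List not meeting exclusion 2 as its own rule, and make the Pathogen and CE Review Plan agree with the SAP.

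The cost is a few lines of SAP text and minor programming. SAP 3.5 allows for amendments approved before database lock, and the SAP 6.1 listing implies that criterion-level data exist. The downside is a slightly smaller CE population.

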7.1.1.2 PTE Visit Clinical Response Assessment

At the PTE visit (Day 14 (\pm 2) days after the subject's first dose of test article), the investigator will determine whether or not the subject meets the criteria of 1 of the following clinical outcomes:

- **Clinical Success:** Sufficient resolution of signs and symptoms at the PTE such that no additional systemic antimicrobial therapy is required for the current infection.
- **Clinical Failure:** No apparent response to therapy or persistence of signs and symptoms of infection or reappearance of signs and symptoms at or before the PTE visit such that use of additional systemic antimicrobial therapy for the current infection is required.
- **Indeterminate:** PTE visit not completed.

For the purpose of analysis, Overall Clinical Response at PTE is determined as follows ([Table 5](#)) from the investigator's assessments at the EOT and PTE Visits as per the CRF:

Table 5 Overall Investigator's Assessment of Clinical Response at PTE Visit

EOT Visit	PTE Visit	Overall Clinical Response at PTE Visit
Success	Success	Success
Success	Failure	Failure
Success	Indeterminate	Indeterminate
Failure	Success	Failure
Failure	Failure	Failure
Failure	Indeterminate	Failure
Indeterminate	Success	Indeterminate
Indeterminate	Failure	Failure
Indeterminate	Indeterminate	Indeterminate

EOT = end of treatment; PTE = post-therapy evaluation.

The Overall Clinical Response is derived based on the “worst case scenario” to accommodate for missing visit assessment and intercurrent events (eg rescue medication at EOT visit). For the ITT and micro-ITT populations, the proportion of subjects with a Clinical Success is defined using the following formula (missing information at the PTE visit will be counted as Indeterminate):

$$\frac{\text{\# of subjects with Clinical Success}}{\text{\# of subjects with Clinical Success} + \text{\# of subjects with Clinical Failure} + \text{\# of subjects with Indeterminate response}}$$

By definition, subjects in the CE-PTE population cannot have an Indeterminate response. Thus, for the CE population, the proportion of subjects with a Clinical Success is defined using the following formula:

$$\frac{\text{\# of subjects with Clinical Success}}{\text{\# of subjects with Clinical Success} + \text{\# of subjects with Clinical Failure}}$$

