7.1.1.3 FFU Visit Clinical Response Assessment

At the follow-up assessment (FFU), subjects will be re-evaluated by the Investigator for clinical response and will be reported for the micro-ITT and CE-FFU population by treatment group.

The investigator will determine whether or not the subject meets the criteria of 1 of the following clinical outcomes:

- **Clinical Success:** Sufficient resolution of signs and symptoms at the Final Follow-up visit such that no additional systemic antimicrobial therapy is required for the current infection.
- **Clinical Failure:** No apparent response to therapy or persistence of signs and symptoms of infection or reappearance of signs and symptoms at or before the Final Follow-up visit such that use of additional systemic antimicrobial therapy for the current infection is required.

- **Indeterminate:** Final Follow-up visit not completed.

Overall (Sustained) Response (based on the investigator's assessment) at FFU is determined as defined in [Table 6](#).

Table 6 Overall Investigator's Assessment of Clinical Response at FFU Visit

Overall Clinical Response at PTE Visit	Clinical Response at FFU Visit	Overall Clinical Response at FFU Visit
Success	Success	(Sustained) Clinical Cure
Success	Failure	Clinical Failure
Success	Indeterminate	Indeterminate
Failure	Success	Clinical Failure
Failure	Failure	Clinical Failure
Failure	Indeterminate	Clinical Failure
Indeterminate	Success	Indeterminate
Indeterminate	Failure	Clinical Failure
Indeterminate	Indeterminate	Indeterminate

PTE = post-therapy evaluation; FFU = Final Follow-up

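### The CE-FFU window waiver in SAP 4.4 2c(ii) looks only at the PTE-visit rating, so some EOT failures that Tables 5 and 6 count as failures drop out of CE-FFU; criterion 3b has a similar gap

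*SAP*

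**What the plan says.** SAP 4.4 makes CE membership cumulative: "To be included in the CE populations, subjects must meet all criteria defined below". The clauses that matter here are these.

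- **CE-PTE, 2b(ii).** The clause that begins "The PTE Visit occurred on Day 14" sets a window of ±2 days and waives it for a subject rated a Clinical Failure at EOT.
- **CE-FFU, 2c(i).** "The Overall (Sustained) Clinical Response (based on the investigator's assessment) at the FFU Visit is not Indeterminate".
- **CE-FFU, 2c(ii).** "The FFU Visit/Call occurred 30 to 37 days from the first dose of test article, unless the subject was considered to be a Clinical Failure". The waiver in full reads "unless the subject was considered to be a Clinical Failure based on the investigator's assessment at the PTE visit".
- **Concomitant antibiotics, 3b.** A subject given a potentially effective systemic antibiotic up to the visit in question is excluded from that CE population. The exception is for subjects "who are a clinical failure on the particular visit and received non-study antibiotics" because the test article did not work well enough.

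The outcome itself is defined across visits. SAP 7.1.1.2 says "The Overall Clinical Response is derived based on the" worst case over EOT and PTE. In Table 5, Failure at EOT gives an overall Failure whatever happens at PTE. Table 6 (SAP 7.1.1.3) starts from the "Overall Clinical Response at PTE Visit" column and carries a failure forward to FFU in the same way. A missed PTE or FFU visit is rated Indeterminate, not Failure.

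**The concern.** The outcome tables and the population rule use different definitions of an earlier failure. Tables 5 and 6 treat a failure at any earlier visit as final. The waiver in 2c(ii) recognises only a failure rated at the PTE visit itself. A woman who fails at EOT and is then not rated a failure at PTE therefore needs an in-window FFU contact to stay in CE-FFU, even though that contact can no longer change her outcome.

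The SAP shows the opposite intent elsewhere. Criterion 2b(ii) keeps EOT failures in CE-PTE without an in-window PTE visit. SAP 4.5 keeps subjects with an unfavourable microbiological outcome at EOT in ME-PTE even if they provide no later culture.

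Criterion 3b adds a second route. Clinical Failure is defined by the need for further antimicrobial therapy, so many failures can be expected to receive it. If the exception applies only to subjects rated a failure at that same visit, rescued subjects who failed earlier are excluded when the later visit is missed or rated Success.

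At stake are the CE-FFU sustained cure rate and, through 3b, the CE-PTE success rate. SAP 7.3.1 reports both with exact confidence intervals, including for differences from nitrofurantoin.

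**Working it through.** The documents give no figure for CE-FFU size, missed visits or sustained cure, so there is no figure to reproduce. The check has three parts.

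**1. One subject, traced through the rules.** She is rated Failure at EOT, misses PTE and FFU, receives no other antibiotic, and otherwise meets the CE criteria.

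- PTE rating: Indeterminate (visit missed).
- Table 5: Failure + Indeterminate = overall Failure at PTE. 2b(i) is met and 2b(ii) is waived, so she is in CE-PTE as a failure.
- Table 6: overall Failure + Indeterminate = Clinical Failure at FFU. 2c(i) is met.
- 2c(ii): no FFU contact on Days 30 to 37, and no failure rating at PTE, so no waiver. She is out of CE-FFU.

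**2. All outcome patterns.** Take EOT (Success, Failure, Indeterminate) × PTE (same three) × FFU (Success or Failure in window, Success or Failure out of window, missed): 3 × 3 × 5 = 45 patterns. Apply 2c(i) and 2c(ii) as written, then again with the waiver keyed to an overall Failure in Table 5. Membership differs in six patterns:

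| EOT | PTE | FFU | Table 5 | Table 6 | As written | Keyed to Table 5 |
|---|---|---|---|---|---|---|
| Failure | Missed | Missed | Failure | Clinical Failure | Out | In |
| Failure | Missed | Success, out of window | Failure | Clinical Failure | Out | In |
| Failure | Missed | Failure, out of window | Failure | Clinical Failure | Out | In |
| Failure | Success | Missed | Failure | Clinical Failure | Out | In |
| Failure | Success | Success, out of window | Failure | Clinical Failure | Out | In |
| Failure | Success | Failure, out of window | Failure | Clinical Failure | Out | In |

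All six are Clinical Failures and none is a cure.

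For subjects given an effective systemic antibiotic, literal 3b acts separately:

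- An EOT failure who misses PTE or is rated Success there leaves CE-PTE.
- An EOT or PTE failure who misses FFU or is rated Success there leaves CE-FFU. For a PTE failure this undoes the waiver that 2c(ii) grants.

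**3. Size, by illustration only.** The CE rate in SAP 7.1.1.2 is successes / (successes + failures); the same form is applied here at FFU. Assumed inputs: 225 planned subjects / 5 groups = 45, all taken as evaluable, with 34 sustained cures and 11 failures. The number of failures dropped, d, is also assumed.

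| d | Rate | Change (points) |
|---|---|---|
| 0 | 34/45 = 75.6% | – |
| 1 | 34/44 = 77.3% | +1.7 |
| 2 | 34/43 = 79.1% | +3.5 |
| 3 | 34/42 = 81.0% | +5.4 |

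If two such arms each lose 2 failures, both move to 79.1% and their difference stays at zero. If one loses 2 and the other none, a difference of 3.5 points appears.

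The window also removes cures. If 3 cures are out of window and 1 failure is dropped, the rate is (34 − 3)/(45 − 4) = 31/41 = 75.6%, the same as with nobody dropped.

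**The case against.** **The clause may mean the overall response.** Table 5 is titled as the overall investigator's assessment, so 2c(ii) could be read that way. But 2b(i) and 2c(i) say Overall where they mean it, 2c(ii) does not, and its twin 2b(ii) plainly refers to a single visit. The literal reading is the stronger one.

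**The Pathogen and CE Review Plan may settle it.** SAP 4.4 sends allocation details there and provides for manual sponsor review before unblinding. That plan is not available here. It may clarify matters, but it cannot be assumed to override an explicit SAP criterion, and membership is first set by program. This objection limits how sure one can be that failures will actually be dropped.

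**Few subjects qualify.** This largely stands. Protocol 8.17 asks subjects who stop treatment to complete later visits if possible, and some FFU contacts may be by telephone. Protocol 7.14 has subjects who need other antibacterials judged Clinical Failures, and the PTE failure definition reaches back before that visit. Many rescued EOT failures who attend PTE should therefore be rated failures there, which triggers the waiver.

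**Stronger readings a reader might infer, which the documents do not support:**

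- *That sustained cures always stay, so the CE-FFU rate is biased upward on balance.* Table 6 contains no window. A cure assessed on Day 29 or Day 38 is still a cure in Table 6, and 2c(ii) drops her with no waiver, while PTE-visit failures stay whatever their FFU timing.
- *That an EOT failure treated elsewhere is necessarily a failure in CE-PTE and absent from CE-FFU.* If she misses PTE or is rated Success there, and that treatment was a potentially effective systemic antibiotic, literal 3b bars her from CE-PTE as well. The contrast holds for the subject traced above, who received none.
- *That the shift can be judged against the 10-point margin.* That margin belongs to the primary ITT test at PTE in SAP 7.2. SAP 7.3.1 sets no margin at FFU. The 82% planning rate in SAP 3.1 is likewise a PTE rate, not a sustained cure rate.

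**Conclusion.** The gap is real on the text. As written, 2c(ii) excludes EOT failures who are not rated a failure at PTE and have no in-window FFU, although Tables 5 and 6 count them as Clinical Failures. Literal 3b does the same to rescued earlier failures, in both CE-PTE and CE-FFU. Relative to a waiver keyed to Table 5, the effect of 2c(ii) on the CE-FFU sustained cure rate can go only one way: up.

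The direction of the net bias from all window exclusions is not established. The size is unknown: about 1.7 to 5.4 points for 1 to 3 failures lost, resting on an assumed 45 evaluable subjects and 34 cures per arm. A distorted comparison with nitrofurantoin needs unequal losses between arms, and nothing in the documents shows that.

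The consequences are confined to secondary CE analyses, which SAP 5.1.4 treats as nominal; Protocol 12.6.2 lists no FFU efficacy analysis at all. The primary ITT endpoint at PTE is untouched. So are the ITT and micro-ITT FFU analyses, which under SAP 5.1.3 use visit data whenever collected.

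**What to change.** Make two wording changes in SAP 4.4:

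- In 2c(ii), make the waiver depend on an Overall Clinical Response at PTE of Clinical Failure as derived in Table 5, in place of the investigator's rating at the PTE visit alone.
- In 3b, make the exception apply to subjects with an Overall Clinical Response of Failure at or before the visit in question, in place of failure on that visit.

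Both are needed. Correcting 2c(ii) alone would leave 3b free to remove the same subjects once they have been rescued. The Pathogen and CE Review Plan and the programmed CE flags should be checked against the new text.

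The cost is an SAP amendment approved before database lock, as SAP 3.5 allows, and no new data. CE rates may come out slightly less favourable.
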